3.4 Exploratory tumor tissue studies and central pathology review

Archival formalin-fixed paraffin-embedded (FFPE) tumor slides will be obtained for central pathology review and molecular studies. Fifteen slides of 10 μ M thickness sections each and 5 slides of 5 μ M thickness sections each will be obtained. Following central pathology review for determining histologic subtype, tumor will be demarcated from adjacent normal tissue on the H+E slide to guide procurement of tumor-enriched samples. The 10 μ M sections will be used for RNA isolation toward gene expression profiling for ~800 cancer-promoting, kinase, DNA-damage repair, bladder cancer-specific and stem cell panel genes by the nanostring platform performed centrally at UAB Cancer Center. A total surface area of tumor 100 mm² is adequate to harvest the necessary amount of RNA (100 ng) using the RNAeasy Mini Kit (Qiagen), and the quality of the RNA will be assessed via the 260/280 ratio using nanodrop. [name] at UAB Radiation Oncology Dept. will perform the nanostring studies as described in previous publications utilizing the nCounter by inputting RNA directly into a hybridization reaction containing color-coded molecular barcodes representing the genes of interest [56].

A minimum of 100 ng of genomic double-stranded DNA (dsDNA) will be isolated from tumor alone for restoration and downstream applications. Genomic DNA will then be isolated using the QIAamp DNA FFPE Tissue Kit on the QIAcube robotic platform (QIAgen, Germantown, MD). dsDNA is quantified using the QuantiT Pico Green dsDNA kit (Invitrogen, Carlsbad, CA) and quality control (QC) is performed by the Illumina FFPE QC kit and real time PCR. If the DNA passes the required QC threshold (5 CT within the QC positive control), the restoration will be performed by using the Infinium HD FFPE Restore kit (Illumina, San Diego, CA). Real time PCR probes for the HPV16 and HPV18 E6 region will be designed using the GeneAssist Copy Number Assay design tool (Invitrogen). Real time PCR quantification of viral load will then be performed using 100 pg of genomic DNA, the HPV16 and HPV18 primer/probe sets and eukaryotic 18S primer/probe set as normalizer in separate reactions. HPV viral load is then calculated as HPV16E6/18S and HPV18E6/18S.

Immunohistochemistry (IHC) will be performed on the 5µM section slides for EGFR, Her2, Her3 and Her4 by previously described methods using appropriate controls.

4. TREATMENTS

4.1 Treatment(s) to be administered

4.1.1 Identity of investigational product

Substance (INN) (Brand name):	Gilotrif
Pharmaceutical form:	Film-coated tablet
Source:	Boehringer Ingelheim Pharma GmbH & Co. KG
Unit strength:	20, 30 and 40 mg film-coated tablets (the dose of Gilotrif in the film-coated tablets is related to the free base equivalent to Gilotrif)
Route of administration:	Oral
Posology	Once daily
Timings	Gilotrif should be taken at least 1 hour before or 2 hours after meal. A missed dose should not be taken within 12 hours of next dose.

4.1.2 Method of assigning patients to treatment groups

This is one arm non-randomized study and all enrolled patients will receive Gilotrif.

4.1.3 Selection of dose(s) in the study

All patients will receive 40 mg of Gilotrif PO qd.

4.1.4 Drug assignment and administration of doses for each patient

4.1.4.1 Gilotrif

Patients will take a single oral dose of Gilotrif each day starting at a dose of 40 mg, continuously, until the development of progressive disease or unacceptable adverse events. Dose escalation and reductions of Gilotrif can occur.

The medication should be taken at the same time each day (\pm 2 hours) without food (at least one hour before or at least two hours after a meal).

Missed doses of Gilotrif can be made up during the same day. Otherwise, the dose will be skipped and patients should take the next scheduled dose at the usual time. Patients with emesis will not take a replacement dose.

If dosing of whole tablets is not possible, Gilotrif tablets can also be dispersed in approximately 100 ml of non-carbonated drinking water. No other liquids should be used.

The tablet should be dropped in the water, without crushing it, and occasionally stirred for up to 15 min until the tablet is broken up into very small particles. The dispersion should be drunk immediately. The glass should be rinsed with approximately 100 ml of water which should also be drunk. The dispersion can also be administered through a naso-gastric tube. Medication will be dispensed in bottles containing 30 tablets at the beginning of each treatment course. For administrative purposes, a treatment course is defined as 28 days. Treatment will start when patient is eligible and enrolled and stop when the patient is diagnosed with disease progression or for any reason detailed in section 3.3.4. Study drug will be prescribed by the investigator and may be dispensed either by the investigator, study coordinator or affiliated pharmacy.

General Properties of Gilotrif

Following oral administration of Gilotrif tablets, the peak Gilotrif plasma concentration occurs in 2-5 hours. Covalent adducts to protein are major circulating metabolites of Gilotrif and enzymatic metabolism of Gilotrif is minimal. In humans, primary excretion is via the faeces (85%). The elimination half-life of Gilotrif is 37 hours. Steady concentration is achieved after 8 days of repeat dosing.

4.1.4.2 Dose reduction for Gilotrif

Treatment related toxicities will be managed by treatment interruptions and subsequent dose reductions of Gilotrif according to the schedule described in Table 4.1.4.1: 1. Dose reductions will apply to individual patients only. Once the dose has been reduced, it cannot be increased later.

To prevent the development of more severe adverse events, treatment related diarrhoea, nausea and vomiting or rash should be managed early and proactive as described in Section 4.2.

Table 4.1.4.1: 1 Dose reduction scheme for Gilotrif

AE type and CTCAE Grade	Action	Dose reduction scheme
Events related to study drug: 
 Diarrhoea Grade 2 persisting for 2 or more consecutive days (48 hours) despite adequate anti-diarrhoeal medication/hydration Reduced renal function to \geq Grade 2 as measured by serum creatinine, proteinuria or decrease in glomerular filtration rate of more than 50% from baseline Any drug related AE Grade \geq3 	
Pause treatment until patient has recovered to Grade \leq1 or baseline¹.
 
Resume treatment at reduced dose according to schedule opposite.
 
If patient has not recovered to Grade \leq1 or baseline¹ within 21 days
	
If patient was receiving 40 mg, resume treatment at a dose of 30 mg.
 
If patient was receiving 30 mg, resume treatment at a dose of 20 mg.
 
If patient was receiving 20 mg, discontinue Gilotrif.

	study treatment will be permanently discontinued ² .	
Acute onset and/or unexplained worsening of pulmonary systems (dyspnoea, cough, fever)	Pause Gilotrif while clinical assessment to exclude ILD is completed.	If ILD is ruled out as a cause of symptoms, grade symptoms and relatedness and report as AEs. If AEs are not related, resume Gilotrif at current dose. If AEs are drug related, follow directions in row above. If ILD is confirmed, discontinue Gilotrif

- 1 Baseline is defined as the CTCAE Grade at the start of treatment
- 2 In the event that the patient is deriving obvious clinical benefit according to the investigator's judgement, further treatment with Gilotrif will be decided in agreement between the sponsor and the investigator.

In the event of any unrelated adverse events, the investigator may choose to interrupt the medication for up to 14 days, but no dose reduction should occur. If the medication is interrupted for more than 14 days, the decision to continue with Gilotrif will be made by the sponsor in agreement with the investigator.

4.1.5 Blinding and procedures for unblinding

4.1.5.1 Blinding

This is a non-randomized one arm study and will not employ any blinding of patients to treatment regimen.

4.1.5.2 Procedures for emergency unblinding

Not applicable

4.1.6 Packaging, labelling, and storage

Medication numbers will be unique to each bottle and will be used for tracking purposes only.

4.1.6.1 Gilotrif

Gilotrif will be supplied as film-coated tablets. Available dosage strengths will be 20, 30 or 40 mg. Tablets will be supplied in HDPE, child-resistant, tamper-evident bottles. .

Bottles/boxes will be labelled according to local regulations and will include the following as a minimum;

- Study number (1200.x)
- Product name (Gilotrif)

- Contents of the bottle (30 tablets)
- Tablet strength (mg)
- Batch number
- Medication number
- Use-by date
- Storage information
- Instructions for use

Sponsor name and address: [name]
Bladder Cancer Director
Dana Farber Cancer Institute
[name]
[name]

- A statement that the medication is for clinical study use only
- A caution statement

A new bottle of medication will be dispensed on day 1 of each course, regardless of the number of tablets remaining in the bottle from the previous course. The patient will initially receive one bottle of 40 mg tablets and in the event that dose reduction is necessary the patient will return to the clinic and new medication will be dispensed.

4.1.7 Storage conditions

Gilotrif will be stored in the original package in order to protect from light. Film-coated tablets are humidity-sensitive; therefore, bottles will be kept tightly closed to protect from moisture. Tablets will be stored according to label instructions.

4.1.8 Drug accountability

Drug supplies, which will be provided by Boehringer Ingelheim, will be kept in a secure, limited access storage area under the storage conditions. A temperature log will be maintained to make certain that the drug supplies are stored at the correct temperature.

A designated person will maintain records of the product's delivery to the study site, the inventory at the site, the use by each patient, and destruction of the unused study drug.

These records will include dates, quantities, batch/serial numbers, expiry ('use by') dates, and the unique code numbers assigned to the investigational product(s) and study patients. The responsible person will maintain records that document adequately that the patients were provided the doses specified by the CSP and reconcile all investigational product(s) received from Boehringer Ingelheim. The responsible person will verify that all unused or partially used drug supplies have been returned by the clinical study patient.

4.2 Management of adverse events, concomitant therapy, restrictions and rescue treatment**4.2.1 Rescue medication, emergency procedures, and additional treatment(s)****4.2.1.1 Rescue medication**

Rescue medications to reverse the actions of Gilotrif are not available. There is no specific antidote for overdosage with Gilotrif. Potential adverse events should be treated symptomatically. Common adverse events of treatment with Gilotrif with specified management recommendations and/or requirements include diarrhoea, and rash/acne. To improve tolerability and the probability of clinical benefit, patients should receive prompt and appropriate supportive care at the first signs of symptoms. Suggested treatments for AEs are described below.

4.2.1.2 Concomitant treatment(s)

Concomitant medications or therapy to provide adequate supportive care may be given as clinically necessary.

After study enrollment, palliative radiotherapy may be given for bone pain or for other reasons (e.g. bronchial obstruction, skin lesions), provided that the total dose delivered is in a palliative range according to institutional standards. The irradiated area cannot be used for tumor response assessment. During palliative radiotherapy, study treatment should be delayed and may be resumed once the patient has recovered from any radiation associated toxicity. If medication is interrupted for more than 14 days, the decision to continue will be made by the sponsor in agreement with the investigator. Continuous interruption of >28 days due to palliative radiotherapy will not be allowed.

All concomitant therapy, including anaesthetic agents, vitamins, homeopathic/herbal remedies, nutritional supplements, will be recorded in the (e)CRF during the screening and treatment period, starting from the date of signature of informed consent, and ending at the EOT visit. After the EOT visit, only concomitant therapy indicated for treatment of an AE has to be reported.

In case of major surgery (as judged by the investigator), it is recommended to stop treatment with Gilotrif around one week prior to the surgery, and to restart treatment after complete wound healing. If Gilotrif is interrupted for more than 14 days, the decision to continue will be made by the sponsor in agreement with the investigator.

4.2.1.3 Emergency procedures

Careful assessment of all patients with an acute onset and/or unexplained worsening of pulmonary symptoms (dyspnoea, cough, fever) should be performed to exclude interstitial lung disease (ILD). Study drugs should be interrupted pending investigation of these symptoms. If interstitial lung disease is diagnosed, study drug will be permanently discontinued and appropriate treatment instituted as necessary.

Patients who present with symptoms of keratitis, such as acute or worsening eye inflammation, lacrimation, light sensitivity, blurred vision, eye pain and/or red eye should be referred promptly to an ophthalmic specialist. If a diagnosis of ulcerative keratitis is confirmed, treatment with Gilotrif should be interrupted or discontinued. If keratitis is diagnosed, the benefits and risks of continuing treatment with Gilotrif should be carefully considered. Gilotrif should be used with caution in patients with a history of keratitis,

ulcerative keratitis or severe dry eye. Contact lens use is a risk factor for keratitis and ulceration.

4.2.2 Management of expected adverse events

Dermatologic adverse events and diarrhoea are the most common side-effects associated with treatment with Gilotrif. Treatment of these side-effects should be proactive and should be started as early as possible after onset of symptoms.

4.2.2.1 Management of diarrhoea and hydration status following treatment with Gilotrif

Diarrhoea occurs at a high frequency and generally begins within 2 weeks of exposure to Gilotrif. Although usually mild to moderate, diarrhoea may lead to dehydration and compel treatment modification or discontinuation, so early management is essential (Table 4.2.2.1: 1). At the time of initiation of treatment with Gilotrif patients should be given a supply of loperamide to keep with them at all times or access to Gilotrif should be confirmed; and patients should be counselled on the appropriate use.

Patients will be advised to drink an adequate amount of fluids to make up for the fluid lost through diarrhoea. (94)

Table 4.2.2.1: 1 Grade specific treatment recommendations for Gilotrif related diarrhoea

Severity (CTCAE Grading)	Description	Intervention concerning Gilotrif treatment	Specific intervention
Mild (Grade 1)	Increase of < 4 stools per day over baseline; mild increase in ostomy output compared with baseline	Continue same dose	Stop laxatives and advise patient to drink at least 8-10 glasses of water or clear fluids per day; 4 mg (2 tablets) of loperamide to be taken immediately, followed by 2 mg (1 tablet) after each loose stool until bowel movements cease for 12 hours
Moderate (Grade 2)	Increase of 4-6 stools per day over baseline; i.v. fluids indicated < 24 hours; moderate increase in ostomy output compared with baseline; not interfering with ADL	Continue same dose unless Grade 2 diarrhoea continues for \geq 2 days (48 hours) in which case treatment will be interrupted until recovered to \leq Grade 1 followed by dose reduction	Continue loperamide; assess for dehydration and electrolyte imbalance; consider IV fluids and electrolyte replacement
Severe (Grade	Increase of \geq 7 stools per day over	Dose interruption until recovered to	See Grade 2; plus: an infectious process

3)	baseline; incontinence; IV fluids > 24 hours; hospitalization; severe increase in ostomy output compared with baseline; interfering with ADL	≤Grade 1 followed by dose reduction*	should be ruled out with stool cultures; aggressive iv fluid replacement ≥ 24 hours; hospitalization to monitor progress; consider prophylactic antibiotics if patient is also neutropenic;
Life threatening (Grade 4)	Life-threatening consequences (e.g. haemodynamic collapse)	Dose interruption until recovered to ≤Grade 1 followed by dose reduction*	See Grade 3

* If despite optimal supportive care and a treatment interruption, diarrhoea does not resolve to CTC AE Grade ≤ 1 within 14 days, treatment with Gilotrif will be permanently discontinued. In the event that the patient is deriving obvious clinical benefit according to the investigator's judgement, further treatment with Gilotrif will be decided in agreement between the sponsor and the investigator.

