5.2.2.2 Adverse event and serious adverse event reporting

Adverse event (AE) monitoring and reporting is a routine part of every clinical trial. Serious Adverse Events (SAEs) are reported by the participating site Lead Investigator within 24 hours to the Clinical Trial Network Monitoring Office (CTNMO) Manager ([name]) by email ([contact]) or by [contact]. The 24 hour paging number for the CTNMO Manager is [contact], [name]. The CTNMO Manager is then responsible for reporting SAEs to the UAB IRB and protocol P.I. in accordance with study-specific requirements. SAEs occurring at CTNMO sites are reported to the UAB IRB as "non-UAB" events.

A serious adverse event (SAE) is defined as any AE which results in death, is immediately life-threatening, results in persistent or significant disability / incapacity, requires or prolongs patient hospitalisation, is a congenital anomaly / birth defect, or is to be deemed serious for any other reason if it is an important medical event when based upon appropriate medical judgement which may jeopardise the patient and may require medical or surgical intervention to prevent one of the other outcomes listed in the above definitions.

An AE will be considered an SAE when the nature or severity of the event is not consistent with the current Investigator's Brochure. It is also the responsibility of the participating site Lead Investigator to report SAEs to the local site IRB and to submit copies of that report to the CTNMO Manager. It is the CTNMO Manager's responsibility to report the SAE to the Clinical Trials Monitoring Committee (CTMC), UAB IRB, sponsor/Principal Investigator ([name] from UAB) and industry funder. This submission of IND Safety Reports will be cross referenced according to local regulations to Boehringer-Ingelheim Investigation New Drug (IND) at the time of submission.

Routine Adverse Event Reporting

All Adverse Events **must** be reported in routine study data submissions. AEs reported must also be reported in routine study data submissions. Safety will be monitored throughout the study by physical examinations, review of adverse events (AEs), and laboratory studies. The frequency of safety monitoring procedures is outlined in Section 5.2.3, 5.2.4 and 5.2.5. Criteria that will be used throughout the study for dose interruption, reduction, and discontinuation of chemotherapeutic agents are specified in Section 4.1.4.2.

Data and Safety Monitoring Plan

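### For drug-related grade 3–4 diarrhoea on 40 or 30 mg, the protocol gives two deadlines for stopping Gilotrif, 14 and 21 days, and does not say which prevails

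*Combined protocol and SAP*

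**What the plan says.** Two places in the protocol govern drug-related diarrhoea of grade 3 or 4.

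- **Section 4.1.4.2, Table 4.1.4.1:1.** The section opens: "Treatment related toxicities will be managed by treatment interruptions and subsequent dose reductions of Gilotrif according to the schedule described in Table" 4.1.4.1:1. The first row of that table lists persistent grade 2 diarrhoea, reduced renal function, and all drug-related events of grade 3 or above. Treatment is paused until recovery to grade 1 or less, or to baseline. The site is then told: "Resume treatment at reduced dose according to schedule opposite". Permanent discontinuation follows only if recovery has not occurred "within 21 days". The steps are 40 to 30 mg and 30 to 20 mg; at the lowest level, "If patient was receiving 20 mg, discontinue Gilotrif".
- **Section 4.2.2.1, Table 4.2.2.1:1.** The grade 3 and grade 4 rows interrupt dosing until recovery to grade 1 or less, then reduce the dose. Both rows carry an asterisk; the grade 2 row does not. The asterisked footnote says that if diarrhoea has not resolved to grade 1 or less "within 14 days, treatment with Gilotrif will be permanently discontinued".

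Both rules carry the same exception: for a patient with obvious clinical benefit, the sponsor and investigator may agree on further treatment.

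**The concern.** Grade 3–4 drug-related diarrhoea falls under both rules, and no sentence says which one prevails. For a patient who recovers after the shorter deadline but within the longer one, one default ends the only study treatment permanently and the other restarts it at a lower dose. Diarrhoea is an expected and frequent effect of this drug (Sections 4.2.2 and 4.2.2.1), although the protocol describes it as usually mild to moderate. With two centres, similar patients could be handled differently by site, and a site that restarts under one table would depart from the other. What is at stake is consistent dosing and time on treatment for a small group of patients.

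**Working it through.** The protocol states no figure for this point, so the check applies both rules to the same patient.

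**Inputs.** From Table 4.1.4.1:1: a 21-day limit and dose steps 40→30, 30→20, 20→stop. From the footnote to Table 4.2.2.1:1: a 14-day limit. Assumptions: both clocks start on the first day of interruption, recovery means grade 1 or less, and the clinical-benefit exception is not used.

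**Rules.** With R the day of recovery, Table 4.1.4.1:1 resumes one level lower if R ≤ 21 and a lower level exists; otherwise it stops. The footnote does the same with R ≤ 14.

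| Dose at onset | R = 1–14 | R = 15–21 | R ≥ 22 |
|---|---|---|---|
| 40 mg | both resume at 30 mg | table: resume at 30 mg; footnote: stop | both stop |
| 30 mg | both resume at 20 mg | table: resume at 20 mg; footnote: stop | both stop |
| 20 mg | both stop | both stop | both stop |

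The rules disagree on 21 − 14 = 7 recovery days at two of the three dose levels, and on none at 20 mg.

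**Clock start.** Neither rule states when counting begins. If the 14-day clock starts d days before the 21-day clock, for example at onset of diarrhoea rather than at interruption, the window is 21 − (14 − d) = 7 + d days: 8 for d = 1, 9 for d = 2. If it starts d days after, for example once optimal supportive care and interruption are both in place, the window is 21 − (14 + d) = 7 − d days: 6 for d = 1, 5 for d = 2, and none at d = 7. So 7 days is the value for a common start, and the uncertainty runs both ways.

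**Recovery standard.** Only Table 4.1.4.1:1 also accepts return to baseline. This matters little, because inclusion criterion 8 (recovery from earlier treatment toxicity) and exclusion criterion 10 (poorly controlled gastrointestinal disorders) largely rule out a starting diarrhoea grade above 1.

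**Does any text set precedence?**

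- *Towards 21 days.* Section 4.1.4.2 sends treatment-related toxicities to its own table. Section 5.2.2.2 says that criteria for interruption, reduction and "discontinuation of chemotherapeutic agents are specified in Section 4.1.4.2". Section 4.2.1.1 introduces the management text with "Suggested treatments for AEs are described below".
- *Towards 14 days.* The footnote is mandatory and specific to diarrhoea, and a safety-first reading takes the shorter limit. Section 4.2.1.1 also speaks of requirements and names diarrhoea. The skin and mucositis sections (4.2.2.2 and 4.2.2.3) send dose adjustment elsewhere; the diarrhoea section does not, and sets its own deadline.
- *Neither way.* Section 4.1.4.2 also points diarrhoea to Section 4.2, but for prevention: "To prevent the development of more severe adverse events, treatment related diarrhoea, nausea and vomiting or rash should be managed early and proactive". The other 14-day limits concern unrelated events (Section 4.1.4.2), palliative radiotherapy and surgery (Section 4.2.1.2), and grade 2 rash (Section 4.2.2.2).

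**Design figures.** The stopping rules do not enter the two-stage calculation. With 13 then 14 patients, stopping at 0 of 13 and success at 4 or more of 27, the probability of success is Σ (x = 1 to 13) P[Bin(13, p) = x] × P[Bin(14, p) ≥ 4 − x]. This gives 0.8011 at p = 0.20, matching the stated 80.1%, and 0.0416 at p = 0.05, within the 5% limit. Both stand whichever deadline applies.

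**The case against.** The strongest reply is that the conflict is uneven and seldom bites. The 21-day figure is an outer limit, so stopping after day 14 does not breach it; only the instruction to resume on recovery goes unmet. Section 3.3.4 also lets the investigator take a patient off treatment for unacceptable adverse events or a change in condition. Restarting on days 15–21 without the exception, by contrast, contradicts the footnote directly. Section 5.2.2.2 adds weekly committee monitoring of adverse reactions and three-monthly calls between sites on managing adverse events.

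Most of this stands, and it narrows the practical effect. It does not remove the inconsistency: discretion to stop is not a default rule, oversight meetings do not set one, and a site that follows Table 4.1.4.1:1 as written still departs from the footnote.

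A reader might instead infer that the documents do choose a number. For 21 days, the pointers to Section 4.1.4.2 are real. But one of them sits in a paragraph on adverse event reporting and speaks of chemotherapeutic agents (Gilotrif is the only study drug), and none overrides a mandatory footnote. For 14 days, one might argue that the specific rule beats the general one. The protocol states no such principle, and Table 4.1.4.1:1 is not silent on diarrhoea: it lists persistent grade 2 diarrhoea under the same 21-day limit. The two arguments lead to opposite answers, so neither settles it.

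**Conclusion.** Wrong as written, as a minor internal inconsistency rather than a questionable design choice. For drug-related grade 3–4 diarrhoea on 40 or 30 mg, with the clinical-benefit exception not used, the two defaults give opposite instructions for recovery on days 15–21. The 7-day width assumes that both clocks start at interruption; it grows or shrinks with the unstated starts. The documents give no frequency for such late recoveries, so no number of patients among the at most 29 enrolled can be estimated.

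Two stronger readings are not supported. One is that patients might be dosed through unresolved severe diarrhoea: both rules hold the drug until recovery. The other is that the primary result is compromised: patients removed for toxicity are still followed until progression or a new agent (Section 3.1), so any effect on PFS6 is indirect.

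**What to change.** State one deadline, one clock start (the first day of interruption) and one recovery standard for grade 3–4 diarrhoea, in identical words in Table 4.1.4.1:1 and in the footnote to Table 4.2.2.1:1. The choice of number belongs to the sponsor's clinicians.

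- If the diarrhoea-specific limit is intended, add to Table 4.1.4.1:1 that for grade 3–4 diarrhoea the 14-day limit in Table 4.2.2.1:1 applies.
- If 21 days is intended, change the footnote to 21 days.

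The cost is a matched wording edit in two tables. It needs no extra visits, procedures or patients, and no change to the statistical design.
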